**Table 2. Study Drug Information**

Investigational Product	Manufacturer	Mode of Administration	Dosage Form	Strength
Venetoclax (ABT-199)	AbbVie	Oral	Film-coated tablet	10, 50, and 100 mg

## 5.8 Randomization/Drug Assignment

This is an open-label study. There is no randomization for this study.

All subjects will be assigned a unique identification number by the IRT at the screening visit (refer to the Operations Manual, Section 6.3). For subjects who rescreen, the screening number assigned by the IRT at the initial screening visit should be used.

## 5.9 Protocol Deviations

AbbVie does not allow intentional/prospective deviations from the protocol except when necessary to eliminate an immediate hazard to study subjects. The investigator is responsible for complying with all protocol requirements, written instructions, and applicable laws regarding protocol deviations. If a protocol deviation occurs (or is identified, including those that may be due to the COVID-19 pandemic), the investigator is responsible for notifying independent ethics committee (IEC)/independent review board (IRB), regulatory authorities (as applicable), and AbbVie.

## 6 SAFETY CONSIDERATIONS

### 6.1 Complaints and Adverse Events

---

#### Complaints

A complaint is any written, electronic, or oral communication that alleges deficiencies related to the physical characteristics, identity, quality, purity, potency, durability, reliability, safety, effectiveness, or performance of a product/device. Complaints associated with any component of this investigational product must be reported to AbbVie.

#### Product Complaint

A product complaint is any complaint related to the biologic or drug component of the product or to the medical device component(s).

For a product this may include, but is not limited to, damaged/broken product or packaging, product appearance whose color/markings do not match the labeling, labeling discrepancies/inadequacies in the labeling/instructions (e.g., printing illegible), missing components/product, device not working properly, or packaging issues.

Product complaints concerning the investigational product and/or device must be reported to AbbVie within 24 hours of the study site's knowledge of the event. Product complaints occurring during the study will be followed up to a satisfactory conclusion.

#### Medical Complaints/Adverse Events and Serious Adverse Events

An adverse event is defined as any untoward medical occurrence in a subject or clinical investigation subject administered a pharmaceutical product and which does not necessarily have a causal relationship with this treatment. An adverse event can therefore be any unfavorable and unintended sign (including an abnormal laboratory finding), symptom, or disease temporally associated with the use of a medicinal (investigational) product, whether or not the event is considered causally related to the use of the product.

Such an event can result from use of the drug as stipulated in the protocol or labeling, as well as from "special situations," which must be reported whether associated with an adverse event or not.

The investigators will monitor each subject for clinical and laboratory evidence of adverse events on a routine basis throughout the study. All adverse events will be followed to a satisfactory conclusion.

An elective surgery/procedure scheduled to occur during a study will not be considered an adverse event if the surgery/procedure is being performed for a pre-existing condition and/or the surgery/procedure has been pre planned prior to study entry. However, if the pre-existing condition deteriorates unexpectedly during the study (e.g., surgery performed earlier than planned), then the deterioration of the condition for which the elective surgery/procedure is being done will be considered an adverse event.

If an adverse event, whether associated with study drug or not, meets any of the following criteria, it is to be reported to AbbVie clinical pharmacovigilance or CRO (as appropriate) as a serious adverse event within 24 hours of the site being made aware of the serious adverse event (refer to Section 4.3 of the Operations Manual for reporting details and contact information):

Death of Subject	An event that results in the death of a subject.
Life-Threatening	An event that, in the opinion of the investigator, would have resulted in immediate fatality if medical intervention had not been taken. This does not include an event that would have been fatal if it had occurred in a more severe form.
Hospitalization or Prolongation of Hospitalization	An event that results in an admission to the hospital for any length of time or prolongs the subject's hospital stay. This does not include an emergency room visit or admission to an outpatient facility.
Congenital Anomaly	An anomaly detected at or after birth, or any anomaly that results in fetal loss.
Persistent or Significant Disability/Incapacity	An event that results in a condition that substantially interferes with the activities of daily living of a study subject. Disability is not intended to include experiences of relatively minor medical significance such as headache, nausea, vomiting, diarrhea, influenza, and accidental trauma (e.g., sprained ankle).
Important Medical Event Requiring Medical or Surgical Intervention to Prevent Serious Outcome	An important medical event that may not be immediately life-threatening or result in death or hospitalization, but based on medical judgment may jeopardize the subject and may require medical or surgical intervention to prevent any of the outcomes listed above (i.e., death of subject, life threatening, hospitalization, prolongation of hospitalization, congenital anomaly, or persistent or significant disability/incapacity). Additionally, any elective or spontaneous abortion or stillbirth is considered an important medical event.

All adverse events reported from the time of study drug administration until 30 days after discontinuation of study drug administration will be collected, whether solicited or spontaneously reported by the subject. In addition, protocol-related serious adverse events and protocol-related nonserious adverse events will be collected from the time the subject signs the study-specific informed consent.

AbbVie will be responsible for Suspected Unexpected Serious Adverse Reactions (SUSAR) reporting for the Investigational Medicinal Product (IMP) in accordance with global and local requirements.

Adverse events will be monitored throughout the study to identify any of special interest that may indicate a trend or risk to subjects.

Worsening of disease or underlying cancer (serious or nonserious events) will be collected as an adverse event due to disease progression on the electronic case report form (eCRF). For serious adverse events with the outcome of death, the date and cause of death will be recorded in the appropriate case report

form (CRF). Deaths due to disease progression that occur within the adverse event reporting period will be collected as an adverse event on the eCRF.

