In Study M14-212, a total of 32 subjects were dosed with venetoclax. The most common adverse events observed in  $\geq 30\%$  of the subjects were nausea (59.4%); diarrhea (56.3%); hypokalemia, vomiting (40.6% each); fatigue, headache (34.4% each); hypomagnesemia (37.5%); febrile neutropenia (31.3%); abdominal pain, cough, hypophosphatemia (28.1% each); epistaxis, hyperphosphatemia, hypocalcemia, malignant neoplasm progression (25.0% each); dyspnea, hypotension, peripheral edema, pyrexia, and pneumonia (21.9% each). Serious adverse events were reported in 27 subjects (84.4%), the most common being febrile neutropenia (28.1%), malignant neoplasm progression (25.0%), and pneumonia (15.6%). No cases of TLS occurred during venetoclax treatment. Efficacy data for Study M14-212 are available for all 32 subjects. The majority (30, 94%) of the subjects had relapsed/refractory AML and a few (2 subjects, 6%) were deemed unfit for intensive therapy. The objective response rate (ORR) was 19% (6 of 32 subjects), with CR in 2 subjects (6%) and CRI in 4 subjects (13%). Anti-leukemic activity was observed in an additional 7 subjects (22%), with  $\geq 50\%$  bone marrow reduction with hematologic recovery in 4 of these subjects.

In Study M14-358, venetoclax was administered daily in a three day ramp-up from 100 to 200 to 400 mg and coadministered with either azacitidine 75 mg/m^2 IV or SC on Days 1 - 7 or decitabine 20 mg/m^2 IV on Days 1 - 5 within each 28 day cycle. Dose adjustments for venetoclax were implemented for

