10.2 Analysis of Adverse Events

10.2.1 Treatment-Emergent Adverse Events

Adverse events (AE) with onset or worsening on or after the first dose of study drug and no more than 30 days after the last dose of study drug are treatment emergent. All summaries of adverse events will include treatment-emergent events (TEAE) only unless specified otherwise.

Adverse event data will be coded using the Medical Dictionary for Regulatory Activities (MedDRA). The version of the MedDRA dictionary that is current at the time of summarization will be applied to the codes prior to summarization. AE rates will then be summarized by system organ class (SOC) and preferred term (PT).

Within each summary the following AE rates will be presented:

- Overall rates: subjects who had at least one AE,
- SOC rates: subjects who had a least one event falling in a given system organ class,

- PT rates: subjects who had at least one event with the given preferred term.

For summaries of AE by National Cancer Institute Common Terminology Criteria for Adverse Events (NCI CTCAE v4.03) grade, at each level of summarization (overall, SOC, and PT) each subject is counted only once at the maximum grade level.

Summaries of SAE are described in Section [10.2.3](#).

The number and percentage of subjects experiencing at least one event for each of the following categories will also be summarized:

- Any TEAE
- TEAE with reasonable possibility of relationship to venetoclax per the investigator.
- TEAE with NCI grade 3 or higher
- TEAE with NCI grade 3 or 4
- TEAE leading to discontinuation of venetoclax
- TEAE leading to venetoclax dose interruption
- TEAE leading to venetoclax dose reduction
- TEAE with reasonable possibility of relationship to the HMA per the investigator
- TEAE leading to discontinuation of the HMA
- TEAE leading to HMA dose interruption
- TEAE leading to HMA dose reduction.

Overview tables with overall rates of each of the above AE types plus treatment-emergent death rates will be prepared for TEAE.

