10.2.2 SAEs (Including Deaths)

Treatment-emergent serious adverse event rates will be summarized by MedDRA system organ class and preferred term as done for adverse events in general. The summaries of SAE data will include tabulations of the following rates:

- All treatment-emergent SAE
- Adverse events resulting in hospitalization
- Adverse events resulting in death.

Treatment Emergent Deaths

Rates of deaths that occur within 30 days of start of treatment and within 30 days following the last dose of study drug will also be summarized.

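### Leukemia progression is collected as an adverse event, and no planned summary gives the overall Grade 3 or higher, treatment-change, serious, hospitalization or fatal event rates without it

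*Protocol*

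**What the plan says.** **Collection.** Protocol Section 6.1 (Medical Complaints/Adverse Events and Serious Adverse Events) brings progression into the adverse event data: "Worsening of disease or underlying cancer (serious or nonserious events) will be collected as an adverse event due to disease progression". It extends this to fatal cases: "Deaths due to disease progression that occur within the adverse event reporting period will be collected as an adverse event on the eCRF". For serious events that end in death it adds that "the date and cause of death will be recorded in the appropriate case report" form, so the cause is available.

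**Analysis.** SAP Section 10.2.1 sets the general rule: "All summaries of adverse events will include treatment-emergent events (TEAE) only unless specified otherwise". Nothing is specified otherwise for progression. The overview rows include "TEAE with NCI grade 3 or higher" and "TEAE leading to discontinuation of venetoclax", with matching rows for interruption and reduction of venetoclax and for all three changes to the hypomethylating agent. SAP Section 10.2.2 adds all serious events, events leading to hospitalization, and "Adverse events resulting in death". It summarizes treatment-emergent deaths by two 30-day windows, one from the start of treatment and one after the last dose, and not by cause. The SAP's safety section does not mention disease progression.

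**The concern.** An overall rate of serious, Grade 3 or higher or fatal events is normally read as a description of how well the regimen is tolerated. Here the same figure also rises when the leukemia progresses. A subject admitted for progression counts in the hospitalization row. One who stops venetoclax because of progression can count as stopping for an adverse event, and one who dies of progression counts as a fatal adverse event.

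This matters more than usual because the study asks whether treatment can be started safely in outpatients (Protocol Section 2.1). The incidence and severity of adverse events is a secondary objective (Section 3.1), and the rate of hospitalization is a safety endpoint (Section 3.4; SAP Section 4.3.4). With no control arm, nothing shows how much of each rate is background progression.

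**Working it through.** The plan gives no expected rate of progression or of other adverse events, so there is no figure of its own to reproduce on this point. The check has three parts.

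**1. Which planned outputs separate progression?**

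| Overall rate | What helps | What is still missing |
|---|---|---|
| Grade 3 or higher | Preferred-term rows | Subject overlap; nonserious events are not in any planned adverse event listing |
| Leading to discontinuation, interruption or reduction | Primary reason for stopping each drug (SAP 8.1), for discontinuation only | The adverse event row itself is unchanged; nothing comparable for interruption or reduction; nonserious events not listed |
| Serious; leading to hospitalization | Preferred-term rows; subject-level listing of serious events (SAP 10.2.4) | A hand count with a classification made after the fact |
| Fatal events | Preferred-term rows; listings of serious events and deaths | A prespecified rate without progression |
| Treatment-emergent deaths | Listing | A split by cause |

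The related-event rows in SAP 10.2.1 probably leave most progression out, but they are not crossed with seriousness, treatment change or death. The Operations Manual (Section 4.2) plans tabulations by grade and relationship, with no progression category.

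**2. Can the rate without progression be obtained by subtracting a preferred-term row?** Study M14-212, described in Protocol Section 2.1, gives a test case.

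- Inputs: 32 subjects; 27 with a serious event; progression as a serious event in 25.0%.
- Reproduced: 27/32 = 84.4%; 0.25 × 32 = 8 subjects.
- No overlap, so that all 8 had progression as their only serious event: (27 − 8)/32 = 19/32 = 59.4%.
- Full overlap, so that all 8 also had another serious event: 27/32 = 84.4%.
- Independence, as an assumption: with r the rate without progression, (1 − r)(1 − 0.25) = 5/32 = 0.156, so r = 1 − 0.156/0.75 = 79.2%, a shift of 84.4 − 79.2 = 5.2 points.

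The two published percentages therefore leave a range of 59.4% to 84.4%. Subtraction does not settle the rate; subject-level data do.

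**3. Size in this study.** The denominator is the planned 60 subjects (Protocol Section 7.3; SAP Section 4.4). If k subjects have progression as their only qualifying event for a given rate, that rate rises by k/60.

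| k (assumed) | Added points |
|---|---|
| 1 | 1.7 |
| 3 | 5.0 |
| 6 | 10.0 |
| 15 | 25.0 |

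An illustration for fatal events, with all counts assumed: 6 deaths not due to progression give 6/60 = 10.0% (exact 95% CI 3.8 to 20.5). Adding 6 progression deaths gives 12/60 = 20.0% (10.8 to 32.3).

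The last line of the table, 15 of 60, corresponds to the 25% seen in M14-212 with no overlap at all. At that progression rate it is the largest possible shift.

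**The case against.** The strongest reply is that little is really hidden. Adverse events are defined regardless of causality, so the overall rows do not claim to be toxicity rates, and related events have their own rows. A progression term would appear as its own preferred-term row, and since a death usually has one fatal event, the fatal table would often reveal the split by itself. SAP Section 10.2.4 lists all data from the serious event records, plus treatment-emergent deaths, so with about 60 subjects the overlap can be resolved by counting. SAP Section 8.1 tabulates the primary reason for stopping each drug. The outcomes closest to the outpatient question are TLS within 7 days, cytopenias, Grade 3 or higher infections and hemorrhages (SAP Table 1), and laboratory TLS (SAP Section 10.3.2). They are defined by specific terms or laboratory values that progression would not normally enter.

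Most of this stands, and it rules out several stronger readings:

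- **That the overall rates could never be corrected.** The listings allow it for serious, hospitalization and fatal events, and the cause of death is collected.
- **That a shift of 5 to 25 points should be expected.** This needs 3 to 15 subjects with no other qualifying event. The 25% comes from a study that was 94% relapsed/refractory and used venetoclax alone, with a 19% response rate. The present subjects are treatment-naïve, and the same combinations gave 70% and 74% CR/CRi in Study M14-358.
- **That the rates are inflated in proportion to treatment failure.** Resistant disease is failure without being progression under the Operations Manual's Table 2, and overlap breaks any proportionality.
- **That comparison with other studies is spoiled.** The SAP plans no such comparison, and M14-212 itself counted progression among its adverse events.

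What the reply does not remove is the absence of any planned overall rate without progression. Counting from listings is a classification made after the data are seen. It also misses nonserious Grade 3 or higher events and nonserious events that changed treatment.

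**Conclusion.** The point holds as a gap in the safety summaries. Collecting progression as an adverse event is a legitimate choice and not an error. The gap is that the SAP carries those events without distinction into the overall rates named above and reports deaths by time window only.

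The size is 1.7 points for each subject whose only qualifying event is progression. The number of such subjects cannot be derived from the documents. It is likely to matter less for the Grade 3 or higher and serious rates, where cytopenias and infections will often put the same subject in the numerator anyway. It is likely to matter more for discontinuation, hospitalization and deaths by time window. That ranking is a judgment; the documents give no data on overlap in this population. The arithmetic assumes 60 treated subjects. The primary remission analysis is not affected.

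**What to change.** In SAP Sections 10.2.1 and 10.2.2:

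- Keep every all-event row as planned.
- For the overall rates of Grade 3 or higher events, events leading to discontinuation, interruption or reduction, serious events, events leading to hospitalization and fatal events, add a parallel row that excludes events recorded on the eCRF as due to disease progression. Name the eCRF item that defines the exclusion.
- Split treatment-emergent deaths in each time window by recorded cause: progression or other.

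The related-event rows need no change, because the causality assessment already does most of this work there.

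The cost is a few table rows and some SAP wording. Protocol Section 6.1 already has sites record the attribution and the cause of death, so no new data or visits are needed. The one drawback is that attribution to progression is the investigator's judgment. Showing both versions keeps that judgment from hiding toxicity.

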### Adverse Events of Special Interest

The following adverse events of special interest will be monitored during the study:

- Cytopenias
- TLS

Subjects will be monitored for blood counts through resolution of cytopenias. Myelosuppression and the related adverse events (thrombocytopenia, anemia, neutropenia, and febrile neutropenia) are common in subjects with AML. Subjects with baseline neutropenia or those with secondary AML might be particularly at high risk for associated adverse events. Additional details are provided in Section 6.2.

If additional dose reductions are thought to be necessary by the investigator, a discussion with the AbbVie medical monitor is required. Subjects experiencing delays for a medical event unrelated to study treatment may delay study treatment up to 4 weeks. Delays greater than 21 days must be discussed with the AbbVie Primary TA MD or a designee.

Anti-infective prophylaxis should be implemented per regional guidelines or institutional standards including appropriate prophylaxis for bacterial, viral, and fungal infections. Potential for drug-drug interactions should be considered and appropriate dose adjustments made if required.

Subjects with resistant disease, based on modified IWG criteria (as described in the Operations Manual, Section 3.16), after End of Cycle 1 will need a bone marrow aspirate to evaluate response after End of Cycle 2. Subjects with resistant disease after end of Cycle 2, based on modified IWG criteria (as described in the Operations Manual, Section 3.16) will need a bone marrow aspirate to evaluate response after end of Cycle 4. Subjects who have not recovered absolute neutrophil count (ANC)  $\geq 500/\mu\text{L}$  within 14 days of drug interruption or require longer duration of interruption between treatment cycles, bone marrow aspirate may be performed, as determined by the investigator, to assess disease status before resuming treatment with next cycle.

Guidelines for TLS management are provided in Section 6.2. Chemistry labs (including creatinine, potassium, calcium, inorganic phosphorus, lactate dehydrogenase, and uric acid) will be performed real-time pre-dose, 4 - 6 hours post-dose, and 24 hours post-dose for each venetoclax dose escalation, and also as deemed necessary per investigator to monitor TLS.

### Adverse Event Severity and Relationship to Study Drug

The investigator will rate the severity of each adverse event according to the National Cancer Institute Common Terminology Criteria for Adverse Events (NCI CTCAE Version 5.0). If a reported adverse event increases in severity, the initial adverse event should be given final outcome date and a new adverse event must be reported to reflect the change in severity. The dates on the adverse events cannot overlap. For all reported serious adverse events that increase in severity, the supplemental eCRFs also need to be updated to reflect any changes due to the increase in severity.

For adverse events not captured by the Common Terminology Criteria, the following should be used:

Grade 1	The adverse event is transient and easily tolerated by the subject (mild).
Grade 2	The adverse event causes the subject discomfort and interrupts the subject's usual activities (moderate).
Grade 3	The adverse event causes considerable interference with the subject's usual activities and may be incapacitating (moderate to severe).
Grade 4	The adverse event is life-threatening and requires urgent intervention (severe).
Grade 5	The adverse event resulted in death of the subject (severe).

The investigator will use the following definitions to assess the relationship of the adverse event to the use of study drug:

Reasonable Possibility	After consideration of factors including timing of the event, biologic plausibility, clinical judgment, and potential alternative causes, there is sufficient evidence (information) to suggest a causal relationship.
No Reasonable Possibility	After consideration of factors including timing of the event, biologic plausibility, clinical judgment, and potential alternative causes, there is insufficient evidence (information) to suggest a causal relationship.

